1. PROTOCOL SUMMARY

1.1. Synopsis

Protocol Title: A Phase 1, Randomized, Open-Label Trial to Evaluate the Safety and Immunogenicity of Pneumococcal Conjugate Formulations in Healthy Adults 18 Through 49 Years of Age

Brief Title: A Phase 1 Study to Evaluate the Safety and Immunogenicity of Pneumococcal Conjugate Formulations in Healthy Adults 18 Through 49 Years of Age

Regulatory Agency Identification Number(s):

US IND Number:	TBD
[EudraCT/CTIS] Number:	N/A
ClinicalTrials.gov ID:	TBD
Pediatric Investigational Plan Number:	N/A
Protocol Number:	C4801001
Phase:	Phase 1

Rationale:

Streptococcus pneumoniae causes invasive (eg, meningitis, sepsis, bacteremic pneumonia) and noninvasive (eg, OM, nonbacteremic pneumonia, sinusitis) disease associated with significant healthcare burden, morbidity, and mortality. 13vPnC (Prevnar 13[®]) was licensed by the FDA and other countries for use in infants and young children for the prevention of pneumococcal disease more than a decade ago. It was subsequently indicated for prevention of pneumonia in adults ≥ 18 years of age. 13vPnC has been introduced into national immunization programs for pediatric and adult populations around the world. 20vPnC was developed to expand protection against pneumococcal invasive disease and pneumonia and has been approved by the FDA and EMA for adults ≥ 18 years of age. 20vPnC contains the identical polysaccharide conjugates and excipients as 13vPnC but with additional conjugate polysaccharides for 7 additional serotypes.

This randomized, open-label Phase 1 study is designed to evaluate the safety and immunogenicity of [REDACTED]

Objectives, Endpoints, and Estimands:

Objectives	Endpoints	Estimands
Primary: To describe the safety profile of [REDACTED] candidates in adults 18 through 49 years of age	Primary: 
Prompted local reactions (redness, swelling, and pain at the injection site)Prompted systemic events (fever, headache, fatigue, muscle pain, and joint pain)AEsSAEs	Primary: In participants receiving the study intervention from each group, the percentage of participants reporting: 
Prompted local reactions within 7 days after administrationPrompted systemic events within 7 days after administrationAEs within 1 month after administrationSAEs within 1 month after administration
Secondary: To describe the immune responses elicited by the [REDACTED] candidates	Secondary: 
OPA titers [REDACTED]	Secondary: In participants complying with the key protocol criteria (evaluable participants) from each group: 
[REDACTED] OPA GMTs 1 month after administration

Overall Design:

This is a Phase 1, multicenter, randomized, open-label study to evaluate alternative [REDACTED] This study will be conducted at investigator sites in the US. Approximately 405 adults 18 through 49 years of age with no history of pneumococcal vaccination will be enrolled. Participants will be enrolled and randomized equally to 1 of 9 groups (45 participants per group): 6 groups will receive 1 of 6 different [REDACTED] candidates and 3 groups will receive either [REDACTED], 13vPnC, or PCV15 (see Study Intervention Groups table below).

There are 3 preformulated products that will be administered at 2 different volumes to create the 6 different [REDACTED] candidates [REDACTED]

Term	Percentage
GMOs	95
Organic	85
Natural	80
Artificial	75
GMOs	90
Organic	80
Natural	75
Artificial	70
GMOs	92
Organic	82
Natural	78
Artificial	73
GMOs	93
Organic	83
Natural	79
Artificial	74

All formulations include AlPO₄.

The key control group will receive polysaccharide conjugate

contained in 13vPnC (Prevnar 13) and 20vPnC (Prevnar 20™). In addition, PCV15 (Vaxneuvance [Merck]) and 13vPnC are both licensed in the US for use in adults and will be included as supplemental controls.

Study Intervention Groups

PFIZER CONFIDENTIAL

Study Intervention Groups

Group	Carrier Protein	Chemistry	Polysaccharide Dose	Dose Volume	n
PCV15 (control)	N/A	N/A	[REDACTED]	0.5 mL	45
13vPnC (control)	CRM ₁₉₇	RAC	[REDACTED]	0.5 mL	45

Abbreviations: N/A = not applicable; RAC = reductive amination chemistry; [REDACTED]

On Day 1 (Visit 1), participants will be assessed for eligibility, have blood drawn for immunogenicity assessments, receive a dose of 1 of the [REDACTED] candidates or controls, be observed for 30 minutes after administration, and receive safety follow-up and e-diary instructions. The study interventions will be prepared and administered by designated staff.

Local reactions (pain, redness, and swelling) occurring at the injection site and systemic events (fever, fatigue, headache, muscle pain, and joint pain) will be prompted for and collected daily in an e-diary from Day 1 through Day 7 after administration of study intervention, where Day 1 is the day of administration. AEs (including nonserious AEs and SAEs) will be assessed for approximately 1 month after study intervention administration (through Visit 2).

At Visit 2 (28-42 days after Visit 1), participants will return for follow-up. Information will be collected from the participants on AEs and e-diary follow-up (as needed), and blood will be drawn for immunogenicity assessments.

Approximately 15 participants from each group will be enrolled at specialty sites that will collect [REDACTED] and approximately 20 mL for sera for OPA and IgG measurements. The remaining participants enrolled at other sites will have 60 mL of blood drawn for sera for OPA and IgG measurements.

Number of Participants:

Approximately 405 participants (approximately 45 per group) will be randomized to study intervention.

Study Population:

Key inclusion and exclusion criteria are listed below (for the full set of criteria, see [Section 5.1](#) and [Section 5.2](#) of this protocol):

Inclusion Criteria

Participants must meet the following key inclusion criteria to be eligible for enrollment into the study:

1. Male or female participants ≥ 18 and ≤ 49 years of age at the time of consent.
2. Adults determined by clinical assessment (including medical history and clinical judgment) to be eligible for the study, including adults with preexisting stable disease (defined as disease not requiring significant change in therapy or hospitalization for worsening disease) within 12 weeks before receipt of study intervention.
3. Female participants of childbearing potential or male participants who are able to father children and are willing to use acceptable methods of contraception for at least 28 days after the dose of study intervention; or female participants not of childbearing potential; or male participants not able to father children.

Note: Female participants of nonchildbearing potential must meet the criteria described in the WOCBP section of the protocol.

4. Capable of giving signed informed consent, which includes compliance with the requirements and restrictions listed in the ICD and in this protocol.

Exclusion Criteria

Participants with any of the following characteristics/conditions will be excluded:

1. History of severe adverse reaction associated with a vaccine and/or severe allergic reaction (eg, anaphylaxis) to any component in pneumococcal conjugate vaccines and any other diphtheria toxoid-containing vaccine.
2. Serious chronic disorder, including metastatic malignancy, severe COPD requiring supplemental oxygen, end-stage renal disease with or without dialysis, cirrhosis of the liver, clinically unstable cardiac disease, or any other disorder that in the investigator's opinion would make the participant inappropriate for entry into the study.
3. Other medical or psychiatric condition including recent (within the past year) or active suicidal ideation/behavior or laboratory abnormality that may increase the risk of study participation or, in the investigator's judgment, make the participant inappropriate for the study.
4. Known or suspected immunodeficiency or other conditions associated with immunosuppression, including, but not limited to, immunoglobulin class/subclass deficiencies, generalized malignancy, HIV infection, leukemia, lymphoma, or organ or bone marrow transplant.

PFIZER CONFIDENTIAL

5. Congenital, functional, or surgical asplenia.
6. Current febrile illness (body temperature $\geq 100.4^{\circ}\text{F}$ [$\geq 38.0^{\circ}\text{C}$]) or other acute illness within 48 hours before study intervention administration.
7. Previous vaccination with any licensed or investigational pneumococcal vaccine, or planned receipt of any licensed or investigational pneumococcal vaccine through study participation.
8. Currently receives treatment with immunosuppressive therapy, including cytotoxic agents or systemic corticosteroids, or planned receipt through the last blood draw (Visit 2). Participants may not be enrolled if corticosteroids were administered within 28 days before study intervention administration. Inhaled/nebulized, intra-articular, intrabursal, or topical (skin, eyes, or ears) corticosteroids are permitted.
9. Receipt of blood/plasma products or immunoglobulin within the 60 days before study intervention administration, or planned receipt during study participation.
10. Receipt of any inactivated or otherwise nonlive vaccine within 14 days or any live vaccine within 28 days before administration of study intervention.
11. Participation in other studies involving investigational drugs, investigational vaccines (except for investigational pandemic vaccines recommended and authorized in this population for emergency use), or investigational devices within 28 days prior to study entry and/or during study participation. Participation in purely observational studies is acceptable.

Study Arms and Duration:

Each participant will participate in the study for approximately 1 month (Visit 1 through Visit 2). The study duration is estimated to be approximately 2 months.

[REDACTED] of the controls [REDACTED], 13vPnC and PCV15) will be administered intramuscularly in the deltoid muscle of the preferably nondominant arm by a site staff member or designee. The preformulated products and controls will be provided to the site by the sponsor.

Study Intervention(s)										
Intervention Name (Formulations)	[REDACTED]		[REDACTED]		[REDACTED]		[REDACTED]		13vPnC (Prevnar 13) 0.5 mL suspension for injection	Vaxneuvance (pneumococcal 15-valent conjugate vaccine) suspension for injection
Arm name (group of participants receiving a specific intervention or no intervention)	[REDACTED]	13vPnC control group	PCV15 control group							
Dose volume	[REDACTED]	0.5 mL administered	0.5 mL administered							
Route of administration	Intramuscular injection									
Use	Experimental	Experimental	Experimental	Experimental	Experimental	Experimental	Control	Control	Control	
IMP or NIMP/AxMP	IMP	NIMP	NIMP							

PFIZER CONFIDENTIAL

Statistical Methods:

The study size of this Phase 1 study is not based on any formal hypothesis test for safety or immunogenicity results. All statistical analyses will be descriptive.

The primary objective is to describe the safety profile of the [REDACTED] candidates; this will be done by summary statistics (including counts and percentages of participants and the associated 2-sided 95% CIs) for local reactions, systemic events, AEs, and SAEs for each study intervention group. With 45 participants per study group, the study will provide a greater than 90% chance of observing at least 1 AE in each group if the true rate is at least 5%.

The secondary objective will be to describe the pneumococcal immunogenicity of the [REDACTED] candidates by summarizing OPA GMTs approximately 1 month after study intervention administration for each group. The corresponding 95% CI for the GMTs will also be provided.

Ethical Considerations:

Participants enrolled in this study are in an age group that is not currently covered by the indication for vaccines containing [REDACTED] conjugate. These participants are relatively healthy and therefore are not recommended for pneumococcal conjugate vaccines. Receiving the [REDACTED] candidates or controls will not interfere with the standard of care for these participants. For those with risk factors for pneumococcal vaccination, the investigator site and ICD will inform participants to seek advice from their healthcare provider regarding the need for immunization after the study.

The study will provide the immune impact of [REDACTED]

[REDACTED] that could potentially benefit adults and children.

The investigational [REDACTED] candidates have not yet been evaluated in clinical studies; therefore, the initial safety data will be generated in this [REDACTED] Phase 1 study.

[REDACTED] The most common AEs noted in adults after vaccination with 20vPnC are primarily related to local reactions (injection site pain, redness, and swelling) and systemic events (fever, headache, fatigue, joint pain, and muscle pain). Safety reviews of data from the 3 completed Phase 3 adult trials has not revealed any unexpected safety concerns.

PFIZER CONFIDENTIAL

1.3. Schedule of Activities

The SoA table provides an overview of the protocol visits and procedures. Refer to the **STUDY ASSESSMENTS AND PROCEDURES** section of the protocol for detailed information on each procedure and assessment required for compliance with the protocol.

The investigator may schedule visits (unplanned visits) in addition to those listed in the SoA table, in order to conduct evaluations or assessments required to protect the well-being of the participant.

Visit Identifier Visit Description	Visit 1	Visit 2	Notes
	Study Intervention Administration	Follow-Up After Study Intervention Administration	
Visit Window (Days)	Day 1	28 to 42 Days After IP Administration	
Obtain informed consent	X		
See Section 8.4.3 for follow-up AE and SAE assessments.Informed consent should be obtained prior to undergoing any study-specific procedures.See Section 10.1.3 for additional information.
Assign participant number via the IRT	X		
Record demography	X		
Perform clinical assessment, including medical history	X		
Record nonstudy vaccinations	X	X	
Record concomitant medication use for treatment of SAEs	X	X	
Obtain oral temperature prior to study intervention administration	X		
Contraception check, if applicable	X	X	
See Section 10.4 for additional information.

PFIZER CONFIDENTIAL

Visit Identifier Visit Description	Visit 1	Visit 2	Notes
	Study Intervention Administration	Follow-Up After Study Intervention Administration	
Visit Window (Days)	Day 1	28 to 42 Days After IP Administration	
Perform urine pregnancy test for female participants of childbearing potential	X		
• See Section 8.4.3 for follow-up AE and SAE assessments.• See Section 8.3.6 for additional information.
Review inclusion and exclusion criteria	X		
• The investigator or designee will inform the participant of the need to use highly effective contraception consistently and correctly until 28 days after the last dose of the study intervention and document the conversation and the participant's affirmation in the participant's chart.
Review continued eligibility		X	
Assign randomization number via the IRT	X		
Specialty sites: Obtain blood sample for immunogenicity assessment	~20 mL (for immunogenicity) [REDACTED]	~20 mL (for immunogenicity) [REDACTED]	
• Blood samples from participants enrolled at specialty sites (n=15/group).• [REDACTED]
Other sites: Obtain blood sample for immunogenicity assessment	~60 mL	~60 mL	
• Blood sample for Visit 1 will be collected prior to administration.
Administer study intervention	X		
• See Section 6.1 for additional information.
Observe and record acute reactions for 30 minutes after study intervention administration	X		
Provide a participant contact card	X		

PFIZER CONFIDENTIAL

Visit Identifier Visit Description	Visit 1	Visit 2	Notes
	Study Intervention Administration	Follow-Up After Study Intervention Administration	
Visit Window (Days)	Day 1	28 to 42 Days After IP Administration	
Provide participant with an e-diary (device or application), thermometer, and measuring device, and instruct to collect prompted local reactions and systemic events	X		
See Section 8.4.3 for follow-up AE and SAE assessments.Participants will record in an e-diary prompted local reactions and systemic events occurring within 7 days after administration. Instruct the participant to complete the e-diary from Day 1 through Day 7, with Day 1 being the day of study intervention administration. Participants will be instructed to contact the study staff or investigator if they experience redness or swelling measuring >20 measuring device units, severe pain at the injection site, or any Grade 4 prompted systemic event.
Review e-diary		X	
Designated site staff will review e-diary data online at frequent intervals (daily is optimal) for the 7 days following administration to evaluate participant compliance and reported events as part of the ongoing safety review.
Collect e-diary or assist the participant to delete the application		X	
Any e-diary devices given to participants are to be collected at Visit 2.
Record and report AEs and SAEs	X-----X		
AEs include nonserious AEs and SAEs.See Section 8.4 for additional information.

PFIZER CONFIDENTIAL

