8.3.2.1. Local Reactions

From Day 1 through Day 7 following study intervention administration at Visit 1, where Day 1 is the day of study intervention administration, participants will be asked to assess redness, swelling, and pain at the injection site and to record the symptoms in the e-diary in the evening. Redness and swelling will be measured and recorded in measuring device (caliper) units (range: 1 to 21+) and then categorized during analysis as mild, moderate, or severe based on the grading scale in [Table 2](#). Measuring device units can be converted to centimeters according to the following scale: 1 measuring device unit = 0.5 cm. Pain at the study intervention injection site will be assessed by the participant as mild, moderate, or severe according to the grading scale in [Table 2](#). The participant will be prompted to contact the investigator if he/she experiences a severe (Grade 3 or above) local reaction to assess the reaction and perform an unscheduled assessment or visit as appropriate. Only an investigator is able to classify a participant's local reaction as Grade 4, after physical examination of the participant or documentation from another medically qualified source (eg, emergency room

or hospital record). If a participant experiences a Grade 4 local reaction, the investigator must immediately notify the sponsor. Site staff will educate the participants regarding signs and symptoms that would prompt site contact. Grade 4 reactions will be collected as AEs on the CRF. The event will be graded using the AE intensity grading scale (Section 10.3.3).

The procedure for notification of the sponsor is provided in the investigator site file or equivalent.

Table 2. Grading Scales for Local Reactions

	Mild Grade 1	Moderate Grade 2	Severe Grade 3^a	Grade 4^b
Redness	5 to 10 measuring device units = >2.0 to 5.0 cm	11 to 20 measuring device units = >5.0 to 10.0 cm	>20 measuring device units = >10.0 cm	Necrosis or exfoliative dermatitis
Swelling	5 to 10 measuring device units = >2.0 to 5.0 cm	11 to 20 measuring device units = >5.0 to 10.0 cm	>20 measuring device units = >10.0 cm	Necrosis
Pain at injection site	Does not interfere with activity	Interferes with activity	Prevents daily activity ^c	Emergency room visit or hospitalization for severe injection site pain

Note: If the size of the redness and/or swelling falls between 2 measuring device units, the higher measuring device unit number will be recorded in the e-diary.

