8.3.2.2. Systemic Events

From Day 1 through Day 7 following study intervention administration at Visit 1, where Day 1 is the day of study intervention administration, participants will be asked to assess headache, fatigue, muscle pain, and joint pain and to record the symptoms in the e-diary in the evening. The symptoms will be assessed by the participant as mild, moderate, or severe according to the grading scale in Table 3 below. Participants will also be instructed to contact site staff or the investigator if they experience any severe (Grade 3 or above) prompted systemic event within 7 days after administration. Study staff may also contact the participant to obtain additional information on Grade 3 events entered into the e-diary.

Only an investigator is able to classify a participant's systemic event as Grade 4, after physical examination of the participant or documentation from another medically qualified source (eg, emergency room or hospital record) or telephone contact with the participant. If a participant experiences a Grade 4 systemic event, the investigator must immediately notify the sponsor. Grade 4 events will be collected as an AE on the CRF. The event will be graded using the AE intensity grading scale (See [Section 10.3.3](#)).

The procedure for notification of the sponsor is provided in the investigator site file or equivalent.

Table 3. Grading Scales for Systemic Events

	Mild Grade 1	Moderate Grade 2	Severe Grade 3^a	Grade 4^b
Fatigue (tiredness)	Does not interfere with activity	Some interference with activity	Prevents daily routine activity	Emergency room visit or hospitalization for severe fatigue
Headache	Does not interfere with activity	Some interference with activity	Prevents daily routine activity	Emergency room visit or hospitalization for severe headache
Muscle pain	Does not interfere with activity	Some interference with activity	Prevents daily routine activity	Emergency room visit or hospitalization for severe muscle pain
Joint pain	Does not interfere with activity	Some interference with activity	Prevents daily routine activity	Emergency room visit or hospitalization for severe joint pain

- a. Prevents daily routine activity, eg, results in missed days of school or work or is otherwise incapacitating; includes use of narcotics for analgesia.

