- b. Grade 4 assessment should be made by the investigator; Grade 4 systemic events will not be collected in the e-diary but will be collected as AEs on the CRF. The intensity of the systemic event should be graded using the AE intensity grading scale in [Section 10.3.3](#).

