8.3.2.2.1. Fever

In order to record information on fever, a digital thermometer will be given to the participant with instructions on how to measure oral temperature at home. Temperature will be collected in the evening daily for 7 days following each study intervention administration (Days 1 through 7, where Day 1 is the day of study intervention administration) and at any time during the 7 days that fever is suspected. The highest temperature for each day will be recorded in the e-diary. In the event of a fever on Day 7, temperature will be collected daily until the fever has resolved (1 day of temperature $<100.4^{\circ}\text{F}$ [$<38.0^{\circ}\text{C}$]) in order to collect a

stop date in the CRF. Participants reporting a fever $>102.0^{\circ}\text{F}$ ($>38.9^{\circ}\text{C}$) will be prompted to contact the study site. Study staff may also contact the participant to obtain additional information if a temperature of $>102.0^{\circ}\text{F}$ ($>38.9^{\circ}\text{C}$) is entered into an e-diary. Temperature will be measured and recorded to 1 decimal place.

Temperatures obtained in degrees Fahrenheit will be programmatically converted to degrees Celsius for reporting. Fever will be grouped into ranges for the analysis according to Table 4.

Table 4. Ranges for Fever

$\geq 38.0^{\circ}\text{C}$ to 38.4°C
$>38.4^{\circ}\text{C}$ to 38.9°C
$>38.9^{\circ}\text{C}$ to $40.0^{\circ}\text{C}^{\text{a}}$
$>40.0^{\circ}\text{C}^{\text{a}}$

Note: Fever is defined as a temperature of $\geq 38.0^{\circ}\text{C}$.

a. Participants reporting a fever $>102.0^{\circ}\text{F}$ ($>38.9^{\circ}\text{C}$) will be prompted to contact the study site.

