- Assign a randomization number and a study intervention container number via the IRT. This must be the last step before proceeding. A site staff member will prepare the study intervention according to the IPM.

After randomization:

- Collect approximately 60 mL of blood prior to study intervention administration.
- Administer a single 0.25-mL or 0.5-mL injection of the assigned study intervention into the deltoid muscle of the preferably nondominant arm (see [Section 6.1](#)).

PFIZER CONFIDENTIAL

After study intervention administration:

- Site staff will observe the participant for 30 minutes after administration of study intervention for any reactions. Record any acute reactions (including time of onset) in the participant's source documents and on the AE page of the CRF, and on the Vaccine SAE Reporting Form, as applicable. Record concomitant medications used to treat SAEs.
- Record concomitant medications used to treat SAEs, if applicable.
- Record AEs and SAEs as described in [Section 8.4](#).
- Explain the e-diary technologies available for this study ([Section 8.3.1](#)) and assist the participant in downloading the study application onto the participant's own device or issue a provisioned device, if required. Provide instructions on the e-diary's use and completion and ask the participant to complete the e-diary from Day 1 through Day 7, with Day 1 being the day of study intervention administration.
- Issue the participant a measuring device to measure injection site reactions and a digital thermometer and provide instructions on their use.
- Ask the participant to contact the investigator site staff or investigator as soon as possible during the 7-day postadministration period if the participant has redness and/or swelling at the injection site measuring >20 measuring device units (>10 cm) or severe injection site pain (prevents daily activity) to determine if an unscheduled visit is required (refer to [Section 8.10.3](#)).
- Ask the participant to contact the investigator site staff or investigator as soon as possible if he or she experiences a fever $\geq 104^{\circ}\text{F}$ ($\geq 40.0^{\circ}\text{C}$) or any severe systemic event from Day 1 through Day 7 after study intervention administration (where Day 1 is the day of administration) to determine if an unscheduled visit is required (see [Section 8.10.3](#)).

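### The Schedule of Activities sets the participant-contact trigger for systemic events at Grade 4, where Section 8 of the protocol acts at severe (Grade 3 or above)

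*Protocol*

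**What the plan says.** **Systemic events.** The e-diary row of the Schedule of Activities (Protocol 1.3) lists the events for which participants are told to contact the site: redness or swelling above 20 measuring device units, "severe pain at the injection site, or any Grade 4 prompted systemic event". Section 8.3.2.2 sets a lower trigger: "Participants will also be instructed to contact site staff or the investigator if they experience any severe (Grade 3 or above) prompted systemic event". The Visit 1 instructions in Section 8.10.1 also ask for contact for any severe systemic event. Section 8.10.3, whose title names a Grade 3 systemic event, requires a telephone contact once a severe systemic event is reported.

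**What Grade 4 means.** Section 8.3.2.2 states: "Only an investigator is able to classify a participant's systemic event as Grade 4". The Table 3 entry for fatigue is "Emergency room visit or hospitalization for severe fatigue", and headache, muscle pain and joint pain follow the same pattern. Footnote b adds: "Grade 4 systemic events will not be collected in the e-diary but will be collected as AEs on the CRF".

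**Local reactions.** Section 8.3.2.1 uses Grade 3: "The participant will be prompted to contact the investigator if he/she experiences a severe (Grade 3 or above) local reaction". The Schedule agrees with it.

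**Fever.** Section 8.3.2.2.1 states: "Participants reporting a fever $>102.0^{\circ}\text{F}$ ($>38.9^{\circ}\text{C}$) will be prompted to contact the study site". The footnote to SAP Table 4 repeats this limit. Section 8.10.1 asks for contact if the participant "experiences a fever $\geq 104^{\circ}\text{F}$ ($\geq 40.0^{\circ}\text{C}$) or any severe systemic event", so that the site can decide on an unscheduled visit. Section 8.10.3 requires telephone contact above 40 °C.

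**The concern.** A Grade 4 trigger cannot serve as an early warning. By the time a systemic event meets the Table 3 description, the participant has already been to an emergency room or been admitted. Section 8.10.1 separately asks for immediate contact in those circumstances, so the Schedule's systemic trigger adds nothing to it. A site that briefs participants from the Schedule alone would leave out the request to call about incapacitating headache, fatigue, muscle pain or joint pain that has not led to hospital care.

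Early contact is useful in this trial. Section 2.3 says that the candidates have not been evaluated in clinical studies. Section 10.1.5.1 says that there is no external data monitoring committee. The Schedule has no visit between Day 1 and the follow-up visit 28 to 42 days later. During the 7-day diary period, participant calls and e-diary review are the main routes by which a severe event reaches the investigator promptly.

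**Working it through.** The systemic trigger is a comparison of text. Table 3 labels Grade 3 as severe, so the two terms can be read as one threshold.

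| Place in the protocol | Who acts | Systemic-event threshold |
|---|---|---|
| 1.3, e-diary note | Participant | Grade 4 |
| 8.3.2.2 | Participant | Severe (Grade 3 or above) |
| 8.10.1, Visit 1 | Participant | Severe |
| 8.10.3 | Investigator or designee, mandatory telephone contact | Severe |

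1. The Schedule stands alone. Both participant instructions in Section 8, and the site obligation in 8.10.3, sit one grade lower.
2. The two local triggers in the same Schedule sentence are redness or swelling above 20 units, and severe pain. In Table 2 both are Grade 3. One sentence therefore uses Grade 3 for local reactions and Grade 4 for systemic events, and no reason is given. A drafting slip is the likeliest explanation.
3. A Grade 3 systemic event calls for contact under 8.3.2.2 and 8.10.1 but not under the Schedule. That is the whole of the gap.

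The fever limits need a little arithmetic, with Celsius = (Fahrenheit − 32) × 5/9:

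- (102.0 − 32) × 5/9 = 38.89, which is 38.9 °C to one decimal.
- (104.0 − 32) × 5/9 = 40.0 °C.
- The limits differ by 104.0 − 102.0 = 2.0 °F, or 40.0 − 38.9 = 1.1 °C. Both conversions are right, so these are two separate limits and not a conversion error.

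| Reading | 8.3.2.2.1 (>38.9 °C): prompt | 8.10.1 (≥40.0 °C): Visit 1 request | 8.10.3 (>40 °C): mandatory call |
|---|---|---|---|
| 39.0 to 39.9 °C | Yes | No | No |
| 40.0 °C | Yes | Yes | No |
| 40.1 °C and above | Yes | Yes | Yes |

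Any reading that meets a higher limit also meets the lower ones, so all three rules can be followed together. At one decimal place, 8.10.1 and 8.10.3 part only at exactly 40.0 °C. Table 4 puts that reading in the >38.9 to 40.0 °C band, which agrees with 8.10.3.

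The documents give no expected rates of Grade 3 systemic events or high fever, so no number of affected participants can be derived.

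**The case against.** The strongest reply on the systemic trigger is that the protocol settles it. Section 1.3 calls the Schedule an overview and refers readers to the assessments section for the detail, and that section is consistent. Participants are also instructed through the Visit 1 steps, which use the right threshold. This shows which text should prevail. It does not make the Schedule entry correct, and the entry is specific enough for a site to follow as written.

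A second reply is that a missed call need not mean a missed contact. Section 8.10.3 makes telephone contact mandatory once a participant reports a severe systemic event. An e-diary entry appears to count as a report, because a mistaken e-diary value is one of the listed reasons for not holding the visit. Section 8.3.1 requires e-diary review at frequent intervals, ideally daily, and gives sponsor staff access at all times. This stands, and it largely limits the effect to the time between a diary entry and its review. Section 8.3.2.2 says only that staff may contact the participant about Grade 3 entries, which is softer than 8.10.3. I take 8.10.3 as governing.

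A reader might infer that the Grade 4 trigger is unworkable because participants cannot assign grades. That goes too far. A participant can recognise an emergency room visit or an admission, and Section 8.3.2.2 lets the investigator classify Grade 4 after telephone contact. The trigger can be followed, but it comes too late to be useful.

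A reader might also infer that the fever limits contradict each other and that contacts between 38.9 and 40.0 °C would be lost. The documents do not support this. The lower limit is a prompt to contact the site, and the higher ones concern whether an unscheduled visit is needed. A participant at 39.5 °C is still prompted. What remains is that the protocol never describes the limits as tiers.

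**Conclusion.** The point holds for the Schedule of Activities: its systemic trigger is one grade too high, out of line with three places in Section 8 and with the local triggers in its own sentence. The fever limits need clarification only, plus one boundary to align.

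The severity is minor. At most, the assessment of an individual severe systemic event is delayed until the e-diary is reviewed. With daily review that is about a day. The protocol sets no maximum interval, so it could be longer at a site that reviews less often. This rests on two assumptions: that sites treat an e-diary entry as a report under 8.10.3, and that they follow 8.10.3 where 8.3.2.2 is permissive.

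It would be wrong to conclude that severe events go unrecorded or that the safety results are biased. Grade 3 systemic events and temperatures are captured in the e-diary whether or not the participant calls. The primary safety percentages, the immunogenicity analysis and the sample size are unaffected.

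**What to change.** 1. In the e-diary note of the Schedule of Activities, replace Grade 4 with severe (Grade 3 or above) for prompted systemic events.
2. State the fever limits as explicit tiers: above 38.9 °C (102.0 °F), the participant is prompted to contact the site; above 40.0 °C (104.0 °F), the site must telephone to decide whether an unscheduled visit is needed.
3. Use the same upper boundary in 8.10.1 and 8.10.3. Above 40.0 °C is the natural choice because it matches Table 4. A reading of exactly 40.0 °C would still draw the lower-tier prompt.

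Two alternatives are less good. Lowering the 8.10.1 limit to 38.9 °C would detach it from the unscheduled-visit rule that it refers to. Moving 8.10.3 to 40.0 °C and above would take it off the Table 4 band.

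The cost is a protocol wording change, a short training note to sites and perhaps a few more telephone calls. Neither the design nor the SAP needs to change.
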